6.1 Effectiveness Endpoints

Unless otherwise specified, all effectiveness endpoints will be summarized for the ITT population.

6.1.1 Primary Effectiveness Endpoints

6.1.1.1 Primary analysis

The primary endpoint of the study is the proportion of treated subjects with improvement in lines and wrinkles of the décolleté by comparing photographs taken at Day 90 (post-treatment) with baseline (pre-treatment) photographs.

Each independent evaluator will assess “Improvement” or “No Improvement” between Photograph 1 (baseline) and Photograph 2 (post-baseline). Photograph 1 will be identified, and the independent evaluators will be blinded to the random distribution of treated versus untreated status of the comparator Photograph 2 (i.e., Day 90 post-treatment among treated subjects or post-baseline for untreated individuals). If photographs are declared as not assessable during the Day 90 assessment session, the evaluators will be instructed to rate the corresponding Photograph 2 as “No Improvement”.

Improvement will be declared if at least two blinded evaluators indicate “Improvement” for the comparator photograph. In case at least two evaluators declare a photograph as not assessable, the corresponding improvement score over all evaluators will be set to missing for the primary analysis.

The point estimate for the proportion of subjects fulfilling the primary endpoint will be described by frequency statistics for the ITT subset.

Effectiveness is established if:

- A. the point estimate is $\geq 65\%$ and
- B. the lower bound of the one-sided 95% Wilson CI is $> 50\%$.

Missing data, including a missing primary endpoint assessment in subjects with unacceptable or missing photographs at baseline or Day 90, will be imputed by multiple imputation. In case of complete data, no multiple imputation will be performed and the primary analysis is based on complete data for the ITT.

Imputation is done 50 times using a fully conditional specification logistic regression method, as implemented in SAS PROC MI with statement FCS LOGISTIC, and will use the investigational site and the baseline characteristics age and BMI as independent variables.

In a first step a total of $m=50$ imputed datasets will be generated, where missing data in the primary endpoint (improvement over all evaluators) is modelled via logistic regression based on input variables site, age and BMI at baseline. CCI

CCI

CCI

CCI response is coded as (0=no response (“no improvement”), 1=response (“improvement”)). The two-sided 90% Wilson CI ([WL, WU]) will be calculated using the following steps, as detailed in [1]:

1. The mean sample response \hat{p}_{Imp} and sample variance \hat{U}_{Imp} ,

$$\hat{U}_{Imp} = \frac{\hat{p}_{Imp} (1 - \hat{p}_{Imp})}{n},$$

will be calculated for each of the $m=50$ imputed datasets with sample size n .

2. The overall mean \bar{p}_m and variance \bar{U}_m over all imputed datasets will be calculated:

$$\bar{p}_m = \frac{1}{m} \sum_{Imp=1}^m \hat{p}_{Imp},$$

$$\bar{U}_m = \frac{1}{m} \sum_{Imp=1}^m \hat{U}_{Imp}.$$

These will be used to obtain B_m ,

$$B_m = \frac{1}{m-1} \sum_{Imp=1}^m (\hat{p}_{Imp} - \bar{p}_m)^2,$$

the between-sample variance.

3. The two boundaries of the 90% Wilson CI (WL and WU) will be calculated as

$$\left[\frac{2\bar{p}_m + \frac{t^2}{n} + \frac{t^2 r_m}{n}}{2 \left(1 + \frac{t^2}{n} + \frac{t^2 r_m}{n} \right)} \pm \sqrt{\frac{\left(2\bar{p}_m + \frac{t^2}{n} + \frac{t^2 r_m}{n} \right)^2}{4 \left(1 + \frac{t^2}{n} + \frac{t^2 r_m}{n} \right)^2} - \frac{\bar{p}_m^2}{1 + \frac{t^2}{n} + \frac{t^2 r_m}{n}}} \right],$$

where t denotes the 0.95 quantile of the t-distribution with degrees of freedom v ,

$$v = (m-1) \left(1 + \frac{1}{r_m} \right),$$

and with

$$r_m = \left(1 + \frac{1}{m} \right) \frac{B_m}{\bar{U}_m}.$$

4. The study is considered successful, and consequently effectiveness is established, if the parameter estimate $\bar{p}_m \geq 65\%$ (condition A), and the lower limit of the 90% Wilson CI as given above, which is equivalent to the lower limit of a one-sided 95% Wilson CI exceeds the margin of 50% (condition B).

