## 11.2.1.1.2 Photographs for Independent, Blinded Evaluation

To assess the proportion of treated subjects with improvement in lines and wrinkles of the décolleté from baseline to Day 90 (i.e., primary effectiveness endpoint) and to Day 180 (i.e., secondary effectiveness endpoint), three independent, blinded evaluators will assess paired, 2D photograph sets of treated subjects and untreated individuals, according to the procedure described below. These evaluators will be experienced, non-treating physicians, who are board-certified in an appropriate specialty (e.g., dermatology, plastic surgery, etc.).

One image set, containing only the frontal view, will be paired as follows:

- Set 1 (treated subjects only): Photograph 1 (baseline) vs. Photograph 2 (Day 90 or Day 180 post-treatment);
- Set 2 (untreated individuals only): Photograph 1 ("baseline") vs. Photograph 2 (post-baseline).

Photograph 1 will be identified, and the independent evaluators will be blinded to the random distribution of treated versus untreated status of the comparator Photograph 2 (i.e., Day 90 or Day 180 post-treatment among treated subjects or post-baseline for untreated individuals).

For each image set, blinded evaluators will assess each photograph and will be asked the following: "Using Photograph 1 as a reference, which of the following best characterizes the change in aesthetic appearance observed in the comparator Photograph 2: Improvement or No Improvement."

Improvement will be declared if at least two blinded evaluators indicate "Improvement" for the comparator photograph.

Additional information on the methodological plan, detailing photograph collection through subsequent presentation to blinded evaluators, will be provided in a supporting document, developed collaboratively between the sponsor and the photography vendor.

This assessment will be proctored by the central photography vendor.

[figure not shown]

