6.1.1.2 Sensitivity analyses

To assess sensitivity of the results, the primary analysis will be repeated for:

- PP population with observed cases,
- ITT with observed cases, and
- ITT with missing value treated as no improvement (worst case analysis).

Observed cases are those not missing on primary analysis.

Additionally, further sensitivity analyses will be performed with regard to image quality as assessed by the central photography vendor. The following analyses will be performed, treating assessments that are based on photographs with not approved image quality as missing:

- PP population with observed cases,
- ITT with observed cases, and
- ITT with missing values imputed by multiple imputation.

For the sensitivity analysis using multiple imputation approach, similar methods as described in section 6.1.1.1 will be performed.

For all other sensitivity analyses, results can be taken directly from the SAS proc freq output:

CCI

, where response_data is the dataset with overall improvement data per subject. The point estimate for the proportion of responders and the lower limit of the two-sided 90% Wilson CI will be used to assess sensitivity.

A sensitivity analysis will not be done, if identical to any other analysis.

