6.1.1.3 Subgroup analyses

Gain or loss of ≥ 2 BMI units from screening to Day 90 will be considered a major protocol deviation. Subjects with gain or loss of ≥ 2 BMI units from screening to Day 90 will be excluded from PP population. The following subgroups will be defined by the change in body weight from screening to Day 90:

- Subjects in ITT population with gain of ≥ 2 BMI units;
- Subjects in ITT population with loss of ≥ 2 BMI units; and
- Subjects in ITT population with change of < 2 BMI units.

The primary endpoint with observed cases will be analyzed in all subgroups, as defined above, with more than five subjects. For all subgroup analyses, the improvement score over all evaluators will be treated as missing, if at least two evaluators declare a photograph as not assessable.

Frequency tables for the proportion of treated subjects with improvement in lines and wrinkles of the décolleté (primary endpoint) will be provided by age categories (\leq median age, $>$ median age), by BMI at baseline in categories (<18.5 , $18.5 - 24.9$, $25 - 29.9$, ≥ 30.0) and by site.

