6.1.2 Secondary Effectiveness Endpoint

The secondary endpoint will only be assessed among subjects reconsented for extended study participation.

The secondary endpoint of the study is the proportion of treated subjects with improvement in lines and wrinkles of the décolleté by comparing photographs taken at Day 180 (post-treatment) with baseline (pre-treatment) photographs.

Each independent evaluator will assess “Improvement”, “No Improvement” or “Cannot Evaluate” between Photograph 1 (baseline) and Photograph 2 (post-baseline). Photograph 1 will be identified, and the independent evaluators will be blinded to the random distribution of treated versus untreated status of the comparator Photograph 2 (i.e., Day 180 post-treatment among treated subjects or post-baseline for untreated individuals). If photographs are declared as not assessable during the Day 180 assessment session, the evaluators will be instructed to rate the corresponding Photograph 2 as “Cannot Evaluate”.

Improvement will be declared if at least two blinded evaluators indicate “Improvement” for the comparator photograph. In case at least two evaluators declare a photograph as not assessable (i.e., “Cannot Evaluate” is ticked), the corresponding improvement score over all evaluators will be set to missing for the secondary analysis. In case one evaluator rates a photograph as “Cannot Evaluate” and the other two evaluators disagree, the overall improvement score will be set to “No Improvement”.

[figure not shown]
The proportion of subjects fulfilling the secondary endpoint will be described by frequency statistics for the ITT subset, including the one-sided 95% Wilson CI.

Missing data, including a missing secondary endpoint assessment in subjects with unacceptable, not assessable or missing photographs at baseline or Day 180, will be imputed by multiple imputation. In case of complete data, no multiple imputation will be performed and the primary analysis is based on complete data for the ITT.

Imputation is done 50 times using a fully conditional specification logistic regression method, as implemented in SAS PROC MI with statement FCS LOGISTIC, and will use the investigational site and the baseline characteristics age and BMI as informing variables. Point estimate and Wilson CI will be calculated with methods as described in Section 6.1.1.1. For implementation, SAS code similar to the statements for the primary endpoint will be used.

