6.4 Special Statistical/Analytical Issues

6.4.1 Discontinuations and Missing Data

Primary and secondary effectiveness endpoints

For analysis of the primary and secondary effectiveness endpoints the following conventions will be applied: if data from the independent evaluators is completely missing (e.g., for all 3 evaluators), the multiple imputation method will be employed as described above for the primary and secondary analysis. For the worst case analysis, the subject will be analyzed as having “no improvement”.

[figure not shown]
The following procedure for incomplete data from the independent evaluators will be applied:

- If the result of two out of three evaluators is missing, the outcome of the subject will be set to missing and the multiple imputation technique will be applied for the primary analysis. The subject will not be included in the observed case analysis and for the worst case analysis, the subject will be analyzed as having “no improvement”.
- If the result of one evaluator is missing and the other two evaluators agree on the assessment “improvement” then the outcome of the subject is set to “improvement” for all analyses.
- If the result of one evaluator is missing and the other two evaluators agree on the assessment “no improvement” then the outcome of the subject is set to “no improvement” for all analyses.
- If the result of one evaluator is missing and the other two evaluators disagree, then the outcome of the subject will be set to missing and the multiple imputation technique will be applied for the primary analysis. The subject will not be included in the observed case analysis and for the worst case analysis, the subject will be analyzed as having “no improvement”.

All other effectiveness data will be analyzed as observed with no imputation of missing values. The denominator for percentages will be all subjects in the respective analysis set or population

(i.e., missing data for binary or categorical variables will be presented as a separate possible category ‘Missing’).

CCI

Adverse events

For any missing data of adverse events, a worst case strategy will be applied for all analysis tables. The intensity will be imputed by the worst intensity “severe”, the causal relationship will be imputed by the worst relationship “related”. Missing data of the outcome will be imputed by “unknown”.

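### Does the Day 90 instruction to rate a not-assessable photograph No Improvement conflict with the rules that set the score to missing?

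*SAP*

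**What the plan says.** **Day 90.** The question in Protocol 11.2.1.1.2 offers two answers for the "change in aesthetic appearance observed in the comparator Photograph 2: Improvement or No Improvement". For a photograph declared not assessable, SAP 6.1.1.1 says "the evaluators will be instructed to rate the corresponding Photograph 2 as “No Improvement". Its next paragraph reads: "In case at least two evaluators declare a photograph as not assessable, the corresponding improvement score over all evaluators will be set to missing". Outcomes made missing in this way are multiply imputed in the primary analysis. SAP 6.1.1.3 repeats the rule for subgroups: the overall score "will be treated as missing, if at least two evaluators declare a photograph as not assessable".

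**Day 180.** SAP 6.1.2 gives evaluators a third answer, Cannot Evaluate. Two or more such ticks make the score missing. If there is one, and "the other two evaluators disagree, the overall improvement score will be set to “No Improvement".

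**Missing reads.** SAP 6.4.1 opens with "For analysis of the primary and secondary effectiveness endpoints the following conventions will be applied". Its rule for a single absent read with a split pair is: "one evaluator is missing and the other two evaluators disagree, then the outcome of the subject will be set to missing". Such a subject is then imputed. The section never mentions not-assessable photographs.

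**Sensitivity analyses.** SAP 6.1.1.2 includes a worst-case analysis that scores every missing outcome as No Improvement. It also includes three analyses "treating assessments that are based on photographs with not approved image quality as missing", where image quality is judged by the photography vendor.

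**The concern.** Two things look wrong.

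First, the Day 90 form has two answers, and one of them must be used for a photograph that carries no information. The rule that sets the score to missing needs a not-assessable declaration, yet the visible text names no field to hold it. If only the ratings reached the database, a photograph that two or three evaluators could not assess would count as a treatment failure instead of being imputed. Day 180 has a tick box for exactly this.

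Second, 6.4.1 covers both endpoints and imputes when one result is missing and the other two evaluators split. SAP 6.1.2 scores one Cannot Evaluate plus a split pair as No Improvement. If a not-assessable read counted as a missing result, the two sections would give different answers for the same subject.

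The verdict depends on a point estimate of at least 65%, and moving subjects from No Improvement to imputed can only help. A rule left open until the ratings are known could therefore favour success.

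**Working it through.** **1. The plan's own figure.** Inputs (SAP 3 and 5.1.1): 80 evaluable subjects, 70% response, success if the estimate is at least 65% and the one-sided 95% Wilson lower bound exceeds 50%.

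Wilson lower bound = [p + z²/2n − z√(p(1−p)/n + z²/4n²)] / (1 + z²/n), with z = 1.645.

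- 52/80: (0.65 + 0.0169 − 0.0893)/1.0338 = 0.559, so both conditions hold.
- The Wilson condition alone needs only 48/80 (0.508; 47/80 gives 0.496). The 65% estimate therefore binds.
- Power = P[Bin(80, 0.70) ≥ 52] = 86.3%, in line with the stated 85% or more. At n = 90 the cut is 59.

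**2. All read patterns.** I = Improvement, N = No Improvement, X = not assessable. Each column applies one reading of the SAP.

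| Pattern | 6.1.1.1 as written | 6.1.2 rules | X treated as missing under 6.4.1 | Ratings only, declarations ignored |
|---|---|---|---|---|
| III, IIN, IIX | I | I | I | I |
| INN, NNN, NNX | N | N | N | N |
| INX | N | N | missing | N |
| IXX, NXX, XXX | missing | missing | missing | N |

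The first two result columns agree in 10 of 10 patterns. The last column differs in three, but it ignores the two-declaration rule stated in 6.1.1.1 and 6.1.1.3. The 6.4.1 column differs in one, INX. There the evaluator did submit a rating, as instructed. Only one of three ratings is Improvement, so the majority rule gives No Improvement, and 6.1.2 says the same explicitly for Day 180.

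**3. What a departure would cost.** Let a be the number of affected subjects, and approximate imputation by the observed rate. The verdict flips when x/n < 0.65 ≤ x/(n−a), with x ~ Bin(n−a, 0.70).

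- n = 80, a = 1: 51/79 = 64.6%, so no flip is possible.
- n = 80, a = 2: only x = 51 flips (51/80 = 63.8%; 51/78 = 65.4%), probability 6.4%.
- n = 90, a = 1: only x = 58 flips (58/90 = 64.4%; 58/89 = 65.2%), probability 5.5%.

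| a | 1 | 2 | 3 | 4 |
|---|---|---|---|---|
| n = 80 | 0% | 6.4% | 7.4% | 15.4% |
| n = 90 | 5.5% | 6.4% | 13.2% | 20.5% |

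**4. Averaged over assumed rates.** The documents give no rate of unassessable photographs, so these are assumptions. Overall flip = Σ P[Bin(n, rate) = a] × flip(a).

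- Two or more declarations in 1% to 3% of pairs: 1.4% to 7.6% (n = 80), 4.0% to 12.3% (n = 90).
- Pattern INX, rate = 3q(1−q)²s, where q is the chance that a single read is unassessable and s the chance that the other two split:
  - q = 1%, s = 0.20: 0.5% (n = 80), 2.5% (n = 90).
  - q = 3%, s = 0.20: 3.2%, 6.6%.
  - q = 3%, s = 0.4626 (independent evaluators: 2p(1−p) with p = 0.6367, which gives 70% majority response): 11.4%, 16.8%.

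The first range applies only if a stated SAP rule is not followed. The second applies only if 6.4.1 is extended to submitted reads.

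**The case for a change.** The strongest argument for a change is that the SAP already contains the cleaner solution and does not use it where it matters most. Day 180 has a tick box and an explicit rule for the split pair. Day 90, which decides success, has neither. SAP 6.4.1 is written for both endpoints and does not exclude not-assessable reads. Every flip computed above runs from failure to success under imputation. The sensitivity analyses do not settle the primary verdict: observed cases are defined by what is missing in the primary analysis, and the image-quality analyses depend on vendor approval, so they miss an approved photograph that evaluators cannot assess.

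The arithmetic stands, and so does the observation that the visible text names no field. That absence is weak evidence. Protocol 8.1 and 11.2.1.1.2 leave the presentation procedure to a separate document, the session is proctored by the photography vendor, and the sentence on transfer of ratings in Protocol 14.2.2 begins mid-sentence where text has been removed. A capture field belongs naturally in a reader manual or transfer specification.

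The claim that a favourable choice is left open does not stand. For two or more declarations the SAP states the outcome twice. For the split pair its specific text gives No Improvement, the less favourable answer. The worst-case analysis scores the imputed subjects as failures, so any dependence of the verdict on them would show in the reported results.

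**Conclusion.** No change to the plan follows. The Day 90 rating instruction and the two-declaration rule work at different levels: one fixes the individual rating, the other overrides the overall score. Applied together they match the Day 180 rules in 10 of 10 patterns. SAP 6.4.1 is coherent when read as covering results that were never submitted, which is what its reference to incomplete data describes. What remains is an unnamed data field and a missing cross-reference affecting one pattern, a gap that analysts following the SAP fill the same way.

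This rests on one assumption that cannot be checked here: each evaluator's not-assessable declaration is recorded apart from the rating. The SAP's rule presupposes it. The flip probabilities, up to 15.4% for four affected subjects of 80, rest on 70% response and on an assumed number of affected subjects. They measure a departure from the plan, not an uncertainty within it. The stated sample size and power are unaffected.

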2.2 Clinical Study Objectives

The objective of this study is to demonstrate the safety and effectiveness of the Octave System for improving lines and wrinkles of the décolleté.

3 Determination of Sample Size

A responder rate of 70% is assumed for the proportion of subjects with improvement from baseline to Day 90, as defined by the correct selection of the Day 90 standardized, photographic images by two of three independent, blinded evaluators. Monte-Carlo simulations were conducted to obtain sample sizes of evaluable subjects required to achieve an improvement rate of \geq 65% and lower bound of 1-sided 95% confidence interval (CI) above 50%. To achieve this threshold with \geq 85% power, a sample size of 80 evaluable subjects will be required. Assuming a maximum attrition of 10 subjects, approximately 90 subjects will be enrolled. In Stage 1, 10 subjects will be enrolled, while all other subjects will be enrolled in Stage 2. Because a sample size of 80 subjects who complete the full Ultherapy treatment session is required, study enrollment will continue until the required number of treated subjects is achieved.

4 Analysis Sets

The following analysis sets will be defined for the statistical analysis of this clinical study:

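### When endpoints are missing, success is a mean of 50 random imputations set against a fixed 65% line; a larger m would nearly remove the small dependence on the seed

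*SAP*

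**What the plan says.** SAP 6.1.1.1 imputes a missing Day 90 outcome (improvement over all evaluators): "Imputation is done 50 times using a fully conditional specification logistic regression method". The outcome "is modelled via logistic regression based on input variables site, age and BMI at baseline". The pooled estimate is the average of the 50 imputed proportions. Step 4 reads "The study is considered successful, and consequently effectiveness is established, if the parameter estimate" is at least 65% (condition A) and the lower limit of the two-sided 90% Wilson interval, which serves as the one-sided 95% limit, is above 50% (condition B).

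Imputation is conditional: "In case of complete data, no multiple imputation will be performed and the primary analysis is based on complete data for the ITT".

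For sample size, SAP section 3 (Determination of Sample Size) and protocol 13.1 say "A responder rate of 70% is assumed for the proportion of subjects with improvement from baseline to Day 90", that "a sample size of 80 evaluable subjects will be required" for at least 85% power, and that a maximum attrition of 10 leads to about 90 enrolled.

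Text directly after the imputation model in 6.1.1.1 is redacted. SAP 6.1.2 refers to SAS statements for the primary endpoint, so code existed, but its content cannot be seen. SAP 6.1.1.2 plans observed-case and worst-case analyses that involve no random draws.

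**The concern.** An average over a finite number of random imputations changes a little each time the procedure is run. In an interval, that noise is partly carried by the between-imputation term and the t quantile. Condition A has no such allowance: the average is simply compared with 65%. If condition A decides success, then in a close trial the confirmatory conclusion can depend on the random number stream and not only on the data. The visible text has no rule for a pooled estimate that lies within Monte Carlo error of 65%. If m or the seed were changed after such a result was known, the change would look data-driven.

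**Working it through.** **Inputs.** From the SAP: m=50; threshold 65%; margin 50%; one-sided 5%; true rate 70%; 80 evaluable; 90 enrolled; at most 10 lost. Not in the documents, so assumed: number and size of sites, site effects, and the pattern of missingness.

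**1. The plan's own power.** With 80 evaluable, condition A needs 0.65 × 80 = 52 responders and condition B needs 48. The exact binomial probability of 52 or more of 80 at a 70% rate is 86.3%, which agrees with the stated 85% or more.

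**2. Which condition binds.** With 90 and complete data, A needs 59 responders and B needs 53. The one-sided 95% Wilson lower limit at 65% with n=90 is 56.4%. With 10 missing, the SAP's imputation version gives about 55.8%. Both are well above 50%, so A decides.

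**3. Monte Carlo error of the pooled estimate.** For k missing of n, ignoring covariates, the between-imputation variance is about

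B = [k·p·q + k²·p·q/(n − k)] / n², and the Monte Carlo SE is √(B/m).

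With p=0.65, p·q=0.2275, n=90 and k=10: B = (2.275 + 0.284)/8100, so √B = 0.0178. Dividing by √50 gives 0.25 percentage points.

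| Missing of 90 | SE at m=50, formula | SE at m=50, simulated with site, age, BMI |
|---|---|---|
| 2 | 0.11 | 0.10 |
| 3 | 0.13 | 0.12–0.13 |
| 5 | 0.17 | 0.16 |
| 10 | 0.25 | 0.23–0.24 |
| 20 (beyond the attrition assumption) | 0.38 | – |

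For scale, one subject is 100/90 = 1.11 points, and the sampling SE is √(0.2275/90) = 5.0 points. Two Monte Carlo SEs with 10 missing are 2 × 0.25 = 0.5 points, which sets the affected band at about 64.5% to 65.5%.

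**4. How often the seed would matter.** The imputation was simulated with posterior draws from a logistic model on site, age and BMI. One setting had 8 equal sites and no covariate effect; another had 10 sites with a logit site SD of 0.3. Both used a light penalty for stability and data missing completely at random.

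- 10 missing: two seeds give opposite verdicts in about 1.3–1.5% of trials at a true rate of 70%, and about 1.8–2.5% at 65%. A repeat run of 4,000 trials per setting gave 1.2–1.3% and 2.0–2.4%.
- 5 missing: about 0.8–1.1% at 70% and 1.3–1.5% at 65%.
- 3 missing: about 0.3–0.5%, with up to 0.7% at a true rate of 65% in the repeat run.
- 2 missing: about 0.5–0.9%.
- None missing: zero.

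The frequency does not fall smoothly with fewer missing, because it depends on where the attainable observed proportions lie relative to 65%: 52/80 is exactly 65.0%, while 55/85 is 64.7%.

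**5. Larger m, 10 missing.** The formula gives 0.0178/√2000 = 0.04 points and 0.0178/√5000 = 0.025 points; simulation gave about 0.02 at m=5000. Seed disagreement falls to about 0.1–0.2% at a true rate of 70%. At 65% the repeat run gave about 0.2–0.3% for m=5000 and 0.35–0.5% for m=2000. These small frequencies are imprecise.

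**The case against.** The strongest reply is that the effect is tiny. The error is less than a quarter of one subject, against a sampling SE of about 5 points. It vanishes with complete data, and its upper end assumes that the maximum attrition occurs. The observed-case and worst-case analyses would be reported beside any borderline result. All of this stands and sets the point's size, although those sensitivity analyses do not settle the primary verdict. Attrition is also not the only source of missing outcomes: SAP 6.1.1.1 and 6.4.1 send unusable photographs and some incomplete ratings to imputation too.

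A reader might infer that the plan fixes no seed, so that two analysts following it exactly could reach opposite conclusions. The documents do not support that. SAS code for the primary endpoint existed and is redacted, and a seed may be in it. A fixed seed would make the result repeatable; inside the band the verdict would still rest on which seed was chosen.

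A reader might also infer that the Day 180 and image-quality imputations share the defect. They do not: neither has a 65% success rule. Nor do the documents support the view that 50 imputations are too few in general. The issue is only the hard cut on the point estimate.

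Finally, no m resolves an exact tie. In a model without covariates, 52 of 80 observed gives a pooled expectation of exactly 65% (probability 5.9% at a true rate of 70%). The site, age and BMI terms will usually move the estimate off the line.

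**Conclusion.** The point holds as a minor one. When any primary outcome is missing, success under SAP 6.1.1.1 turns on whether a mean of 50 random imputations reaches 65%. With 10 of 90 missing, the verdict is seed-dependent only within about ±0.5 points of 65%, and two seeds would disagree in roughly 1.3–2.5% of trials. The standard error follows from the SAP's own figures by the formula above. The disagreement frequencies rest on assumed sites, site effects and random missingness, and would grow if more than 10 outcomes were missing. Neither the validity of the interval nor the stated power is in question.

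**What to change.** Before ratings are received, change SAP 6.1.1.1 as follows:

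- Replace m=50 by m=5000 (at least 2000). The pooling formulas stay as they are.
- Confirm that one fixed seed is specified, or state one if it is not already in the redacted code.
- Report the Monte Carlo SE, √(B/m), beside the pooled estimate.

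Using the same m for Day 180 and the image-quality analysis is optional, for consistency only. The cost is computing time on about 90 rows; conduct, sample size and success criteria do not change.

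### The degrees of freedom for the multiple-imputation Wilson interval lack a square on (1 + 1/r), so the interval is slightly too wide and a check program using the correct form will not reproduce it

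*SAP*

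**What the plan says.** SAP section 6.1.1.1 handles a missing primary outcome by multiple imputation: "In a first step a total of $m=50$ imputed datasets will be generated". From these it takes the mean proportion p̄, the mean within-imputation variance Ū and the between-imputation variance B, and sets r_m = (1 + 1/m)B/Ū. Step 3 gives Wilson-type bounds in which t "denotes the 0.95 quantile of the t-distribution with degrees of freedom" v, with v = (m−1)(1 + 1/r_m) and no exponent on the bracket. Step 4 ties condition B, a lower limit above 50%, to this interval; condition A requires p̄ of at least 65%.

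The same interval is used elsewhere. For Day 180, section 6.1.2 states: "Point estimate and Wilson CI will be calculated with methods as described in Section 6.1.1.1". Section 6.1.1.2 applies similar methods in the image-quality sensitivity analysis that uses multiple imputation. With complete data, no imputation is done and the formula is not used.

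**The concern.** The bounds in step 3 rest on a total variance with two parts, Ū and (1 + 1/m)B. Only B is estimated on m−1 degrees of freedom, and the effective degrees of freedom of the sum depend on the square of the share that B contributes. The printed formula has that share to the first power.

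This is the formula for the confirmatory interval, and the SAP is meant to guide programming. If it is coded as printed, the reported limits are wrong, always on the wide side. An independent programmer using the correct degrees of freedom would not reproduce them. Correcting the formula after results are known would also mean changing a prespecified confirmatory method.

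**Working it through.** **Inputs.** From SAP 6.1.1.1: m = 50, the 0.95 quantile, the definition of r_m, and conditions A (65%) and B (50%). From SAP section 3: 80 evaluable subjects, about 90 enrolled, attrition of at most 10, true rate 70%. The documents do not give r. I assume r ≈ k/(n−k) for k missing of n, so 10 of 90 gives 10/80 = 0.125. A simple imputation simulation supports this (10 of 90 missing: mean r 0.127, 95% of runs between 0.08 and 0.18).

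**The plan's own figure.** The SAP says: "A responder rate of 70% is assumed for the proportion of subjects with improvement from baseline to Day 90". With 80 subjects, condition A needs 52 responders (52/80 = 65%) and condition B needs 48. Condition A therefore decides. The exact binomial probability of 52 or more of 80 at 70% is 86.3%, so the stated power of at least 85% reproduces.

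**The interval apart from v.** Start from (p̄ − p)² = t²(1 + r)p(1 − p)/n and write c = t²(1 + r)/n. This gives p²(1 + c) − p(2p̄ + c) + p̄² = 0, whose roots are exactly the SAP's bounds. At r = 0 they reduce to the ordinary Wilson form. The rest of step 3 is sound.

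**The degrees of freedom.** The bounds use T = Ū + (1 + 1/m)B = Ū(1 + r). Treat Ū as fixed and B as a scaled chi-square on m−1 degrees of freedom:

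- Var(T) = (1 + 1/m)² · 2B²/(m−1)
- v = 2T²/Var(T) = (m−1)[T/((1 + 1/m)B)]²
- T/((1 + 1/m)B) = Ū(1 + r)/(Ūr) = 1 + 1/r
- hence v = (m−1)(1 + 1/r)²

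One million simulated values of T gave an effective v of about 3965 at r = 0.125 (squared form 49 × 9² = 3969; printed form 49 × 9 = 441). At r = 0.5 they gave about 442 (squared 49 × 3² = 441; printed 49 × 3 = 147).

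**Effect on the lower limit** (p̄ = 0.65; printed / squared):

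| n | r | v | t | Lower limit, % | Difference, points |
|---|---|---|---|---|---|
| 90 | 0.05 | 1029 / 21609 | 1.64634 / 1.64492 | 56.177 / 56.185 | 0.008 |
| 90 | 0.125 | 441 / 3969 | 1.64832 / 1.64524 | 55.849 / 55.866 | 0.017 |
| 90 | 0.25 | 245 / 1225 | 1.65110 / 1.64610 | 55.326 / 55.356 | 0.030 |
| 90 | 0.5 | 147 / 441 | 1.65529 / 1.64832 | 54.356 / 54.401 | 0.046 |
| 90 | 1.0 | 98 / 196 | 1.66055 / 1.65267 | 52.640 / 52.700 | 0.060 |
| 80 | 0.125 | 441 / 3969 | 1.64832 / 1.64524 | 55.281 / 55.300 | 0.019 |
| 80 | 1.0 | 98 / 196 | 1.66055 / 1.65267 | 51.881 / 51.944 | 0.063 |

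For an assumed 40 subjects at Day 180 with r = 0.5, the limits are 48.98% and 49.04%.

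**When condition B could decide.** At p̄ = 0.65 the lower limit equals 50% when 0.15² = t²(1 + r)(0.25)/n, that is, 1 + r = 0.09n/t². For n = 80 this is 7.2/t², so r is about 1.60 (printed) or 1.62 (squared). For n = 90 it is about 1.92 or 1.94. With r = k/(n−k), r = 1.60 means 1.60/2.60, or about 62%, of outcomes missing.

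**The case against.** The alleged defect is a single superscript in a formula read from a PDF by a program. Other squares in the same step survived, including those on bracketed terms, but that does not prove this one was read correctly. SAP section 2.1 gives the Day 28 call window with a plain plus sign where protocol section 8.1 has plus or minus, which could be another lost mark. The source page must therefore be checked.

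The SAS code is redacted, so the program may already use the squared form. In that case the outputs would be right and only the printed line would need correcting. A checker who codes the SAP as printed would also reproduce the SAP's limits; the mismatch arises only when one side uses the correct form.

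The consequence for inference is negligible. The shift is about 0.02 points at planned attrition, it is conservative, and condition A decides. Day 180 has no success threshold, so only a reported limit moves there. The observed-case and worst-case analyses do not use the formula, and neither does the primary analysis if data are complete.

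All of this stands as a limit on the size and reach of the point. None of it makes the printed formula right.

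**Conclusion.** The concern holds, as a minor point. The formula as printed does not follow from the SAP's own definitions; the squared form does, and simulation confirms it. At the planned attrition the lower limit is too low by 0.017 to 0.019 points (n = 90 and 80), and by up to about 0.06 points at r = 1. A limit reported to one decimal can still differ: 55.849% rounds to 55.8 and 55.866% to 55.9.

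The error cannot create a false success. The primary verdict would change only if the observed rate sat at the 65% threshold with more than about 60% of outcomes missing. Sample size is unaffected.

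The conclusion assumes that the exponent is also absent from the source page. The figures rest on r ≈ k/(n−k); the Day 180 count of 40 and its r of 0.5 are illustrative.

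**What to change.** Check the source page of SAP section 6.1.1.1, step 3. If the square is absent, write v = (m−1)(1 + 1/r_m)². Confirm that the program uses this form in the primary analysis, the Day 180 analysis and the image-quality analysis with multiple imputation. Protocol section 13 allows the SAP to be updated; make the change before the Day 90 database close, while no results are known. The cost is one exponent in the SAP and, if the program follows the printed text, one in the code.
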